6.3. Post-Treatment/Treatment-Free Follow-up Assessments

6.3.1. Follow-Up Assessments

For subjects with known bridging fibrosis or cirrhosis, study drug discontinuation with treatment-free follow-up is contraindicated due to the potential risk of exacerbation of hepatitis in the setting of low hepatic reserve which could lead to decompensation. Subjects with bridging fibrosis or cirrhosis should be placed on commercially available HBV therapy following study drug discontinuation.

Subjects who have received at least one dose of study drug and permanently discontinue study drug will be followed for 24 weeks off treatment or up to initiation of active treatment, whichever occurs first. The treatment-free follow-up period could occur for early discontinuation subjects or at Week 192 study completion.

For those subjects who remain off treatment, the following evaluations are to be completed every 4 weeks through the Week 24 Follow-Up Visit (Follow-Up Weeks 4, 8, 12, 16, 20 and 24). Each follow up visit should be conducted within ± 3 days from the protocol-specified visit date, calculated from the date of last dose.

- Symptom-directed physical examination, including vital signs
- Body weight and height
- Blood samples for:
 - Serum chemistry and liver function tests, including albumin, alkaline phosphatase, AST, ALT, total bilirubin (reflex to direct [conjugated] bilirubin if total bilirubin $> 1.5 \times$ ULN), bicarbonate, BUN, calcium, chloride, CPK, creatinine (and calculated creatinine clearance), glucose, LDH, magnesium, phosphorus, potassium, sodium, uric acid, and amylase (reflex lipase testing if total amylase is $\geq 1.5 \times$ ULN)
 - Hepatitis B serology (HBeAg and HBsAg; reflex HBeAb and HBsAb if Ag negative) (Follow-Up Week 24 only)
 - Plasma HBV DNA (PCR method)
 - Serum and plasma for storage (for potential pharmacokinetic and/or virologic assays, including resistance surveillance, HBsAg and HBeAg quantification and compliance assessment)
 - Prothrombin time (PT), international normalized ratio (INR) (reflex test in case of post-treatment exacerbation of hepatitis)
- Review of AEs and concomitant medications

Subjects experiencing post-treatment exacerbation of hepatitis during the 24-week post-treatment period should be followed weekly until their ALT levels return to Grade 2 or baseline, as described in the Toxicity Management section of the protocol (Section 7.6.)

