7.3. Serious Adverse Events

A **serious adverse event** (SAE) is defined as follows:

Any adverse drug experience occurring at any dose that results in any of the following outcomes:

- Death
- Life-threatening situation. Life-threatening means that the subject was at immediate risk of death from the reaction as it occurred.

- In-patient hospitalization or prolongation of existing hospitalization (excluding those for study therapy or placement of an indwelling catheter, unless associated with other SAEs)
- Persistent or significant disability/incapacity
- Congenital anomaly/birth defect in the offspring of a subject who received study drug
- Other: medically significant events that may not be immediately life-threatening or result in death or hospitalization, but based upon appropriate medical and scientific judgment, may jeopardize the subject or may require medical or surgical intervention to prevent one of the outcomes listed above
- Examples of such events are as follows:
 - Intensive treatment in an emergency room or at home for allergic bronchospasm
 - Blood dyscrasias or convulsions that do not result in hospitalization
 - Development of drug dependency or drug abuse

For the purposes of this study, in addition to the above criteria, the following must be reported as SAE's:

- Serum ALT $> 2 \times$ baseline and $> 10 \times$ ULN, with or without associated symptoms.
- Confirmed ALT elevation (defined as 1-grade shift or $2 \times$ previous value) associated with confirmed changes outside of the normal range in other laboratory parameters suggestive of worsening hepatic function (abnormal PT ≥ 2 seconds or INR ≥ 0.5 over baseline, abnormal serum albumin ≥ 1 g/dL below baseline or elevated serum lactate levels (if available), defined as $2 \times$ ULN per the Adult AIDS Clinical Trials Group (AACTG) guidelines).
- Any clinical manifestations of hepatic decompensation (variceal bleeding, hepatic encephalopathy, or worsening of ascites requiring diuretics or paracentesis).

Clarification of Serious Adverse Events

- Death is an outcome; therefore, not an AE in itself; the SAE is the condition(s) that leads to death.
- The subject may not have been on study drug at the occurrence of the event. Dosing may have been given as treatment cycles or interrupted temporarily before the onset of the SAE, but may have contributed to the event.

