7.6.6. On-Treatment ALT Flare and Post-Treatment Exacerbation of Hepatitis Management

For subjects with bridging fibrosis or cirrhosis, study drug discontinuation with treatment-free follow-up is contraindicated due to the potential risk of exacerbation of hepatitis in the setting of low hepatic reserve which could lead to decompensation. Subjects with bridging fibrosis or cirrhosis should be placed on commercially available HBV therapy following study drug discontinuation.

On-Treatment ALT Flare and Post-Treatment Exacerbation of Hepatitis are defined as:

- Serum ALT $> 2 \times$ baseline and $> 10 \times$ ULN, with or without associated symptoms OR
- Confirmed ALT elevation (defined as 1-grade shift or $2 \times$ previous value) associated with confirmed changes outside of the normal range in other laboratory parameters suggestive of worsening hepatic function (abnormal PT ≥ 2 seconds or INR ≥ 0.5 over baseline, abnormal serum albumin $\geq 1 \text{ g/dL}$ below baseline or elevated serum lactate levels (if available), defined as $2 \times$ ULN per the Adult AIDS Clinical Trials Group (AACTG) guidelines).

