7.6.6.1. Management of ALT Flare in Subjects Receiving Study Medication

If laboratory results indicate (1) elevation of ALT $> 2 \times$ baseline and $> 10 \times$ ULN OR (2) abnormal laboratory parameters suggestive of worsening hepatic function (abnormal PT ≥ 2 sec above baseline, INR ≥ 0.5 above baseline, abnormal albumin ≥ 1 g/dL decrease from baseline or elevated serum lactate levels $> 2 \times$ ULN along with any ALT elevation (i.e., grade shift or $2 \times$ previous value), the following is recommended:

- Schedule the subject to return to the clinic as soon as possible and ideally no later than one week after the initial labs were drawn. During the visit, perform a clinical assessment of the subject. The assessment should include a physical examination and evaluation of the subject's mental status.
- Draw blood samples, request lactate testing and send for confirmation of elevated serum transaminases (ALT/AST), total bilirubin and PT/INR, and albumin. [Note: If, in the investigator's judgment, the central laboratory cannot provide adequate turn around time, the confirmation test may also be performed at a local laboratory. However, the central laboratory results are considered definitive].

If the elevations are confirmed, request the central clinical laboratory to conduct reflex testing for serum HBV DNA, HBV serology (HBeAg, HBeAb, and HBsAg), HDV, HAV IgM, and HCV serology.

Based on the results of the confirmatory tests, the following treatment modifications are recommended:

Elevated Liver Enzymes, Normal Bilirubin, Normal PT/INR, Normal Albumin, Normal Lactate

If ALT and/or AST levels are elevated (i.e., $> 2 \times$ baseline and $> 10 \times$ ULN) but total bilirubin and PT/INR, albumin and lactate are normal, the subject may remain on study medication and should be monitored every week until ALT/AST return to normal or baseline levels. During monitoring:

- If ALT/AST levels decline within 4 weeks, the subject should remain on study and return to the clinic per protocol.
- If after 4 weeks of monitoring, ALT/AST values remain elevated (e.g., $> 2 \times$ baseline and $> 10 \times$ ULN) or have worsened, with bilirubin $\leq 2.5 \times$ ULN, PT $\leq 1.5 \times$ ULN, or abnormal albumin or lactate levels, the investigator should consult with the Gilead Medical Monitor.

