7.6.6.2. Management of Exacerbation of Hepatitis in Subjects Who Have Discontinued Study Medication

If laboratory results indicate (1) an ALT elevation $> 2 \times$ baseline and $> 10 \times$ ULN OR (2) abnormal laboratory parameters suggestive of worsening hepatic function (abnormal PT ≥ 2 secs above baseline, abnormal albumin ≥ 1 g/dL below baseline or elevated lactate levels $> 2 \times$ ULN) along with any ALT elevation (i.e., 1 grade shift or $2 \times$ previous value) and the subject is on no post-study therapy for HBV, the following is recommended:

- Schedule the subject to return to the clinic as soon as possible and ideally no later than 1 week after the initial labs were drawn. During the visit, perform a clinical assessment of the subject. The assessment should include a physical examination and evaluation of the subject's mental status.
- Draw blood samples and request lactate testing and confirmation of elevated serum transaminases (ALT/AST), bilirubin, PT/INR, and albumin. [Note: If, in the investigator's judgment, the central lab cannot provide adequate turn around time, the confirmation test may also be performed at a local lab. However, the central lab results are considered definitive].

- If the elevations are confirmed (e.g., ALT > 2 × baseline and > 10 × ULN) OR (2) abnormal laboratory parameters suggestive of worsening hepatic function (abnormal PT ≥ 2 secs above baseline, abnormal albumin ≥ 1 g/dL below baseline, or elevated lactate levels > 2 × ULN) along with any ALT elevation (i.e., 1 grade shift or 2 × previous value), request the clinical laboratory to conduct reflex testing for serum HBV DNA, HBV serology (HBeAg, HBeAb, and HBsAg), HDV, HAV IgM and HCV. If serum HBV DNA is increasing, the investigator should consider immediate initiation of approved therapy.
- The subject should be followed until the abnormal ALT/AST values, PT/INR, albumin or lactate laboratory parameters return to normal or baseline up to a maximum of 6 months after the initial occurrence of the event. Refer to [Appendix 6](#) for specific guidelines for the management of symptomatic and asymptomatic hyperlactatemia.

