- g HBeAg and HBsAg and, if negative, reflex HBeAb and HBsAb, respectively.
- h Determination of HBV viral genotype (A–H) will be performed at the Baseline Visit for all subjects. Resistance surveillance will be conducted at Baseline for all subjects, and attempted for all viremic subjects (HBV DNA \geq 400 copies/mL [69 IU/mL]) at Weeks 48, 96, 144, and 192, as well as at the Early Discontinuation Visit, if applicable.
- i Including estimated creatinine clearance, by the Schwartz Formula (2 to <12 years old).
- j PT/INR will be performed at the Screening and Baseline Visits, then as a reflex test in subjects experiencing exacerbation of hepatitis thereafter.
- k For females of childbearing potential only; a serum β -HCG pregnancy test will be performed at Screening, Baseline, Weeks 48, 72, 192 and Early Study Drug Discontinuation/End of Treatment Visit (if applicable). Urine pregnancy testing will be performed at all other study visits through the end of the study including the Extension Phase. A positive urine pregnancy test must be confirmed immediately with a serum pregnancy test.
- l Blood (serum and plasma) collected for long-term storage and possible future testing (e.g., pharmacokinetic and/or virologic analysis).
- m DEXA scan will be performed between the Screening and Baseline Visits, and must be performed prior to randomization and receipt of study drugs. All other DEXA scans must be performed within \pm 10 days of the scheduled study visits. DEXA scan will be performed at the time of switch for subjects switching from placebo to tenofovir DF, unless the most recent DEXA scan was performed within 12 weeks earlier.
- n Specimens for bone biochemical markers must be collected in the morning in a fasted state, or, if fasting is not feasible, within two hours of the time of day that the Baseline Visit specimen was collected. For example, if the bone biochemical markers were drawn at 7:00 AM for the Baseline Visit, they must be drawn no earlier than 5:00 AM and no later than 9:00 AM for Week 24, 48, 72, 96, and subsequent specified visits. Bone biochemical markers will also be collected at the time of switch for subjects switching from placebo to tenofovir DF if not done within 12 weeks prior to switch. Bone biochemical markers will also be collected at the Screening Visit; the mean of the Screening and Baseline Visit values will constitute the study baseline, to which subsequent values will be compared.

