7.2.3. ALT Flare and Exacerbation of Hepatitis

Summaries of the incidence of ALT flare and exacerbation of hepatitis will be provided by treatment group using the subjects in the Safety Analysis Set for on-treatment occurrences during the double-blind phase and off-treatment occurrences. On-treatment occurrences in the double-blind phase will be defined as occurrences in the period between the first dose of blinded study drug to the minimum of the last dose date of blinded study drug + 3 days and first dose date of open-label study drug, if applicable, for those who discontinued blinded study drug permanently. Off-treatment occurrences will be defined as occurrences after the last dose of study drug + 3 days. A supportive listing will also be generated.

Incidence of ALT flare and exacerbation of hepatitis is defined as:

- Serum ALT $> 2 \times$ study baseline and $> 10 \times$ ULN, with or without associated symptoms

OR

- Confirmed ALT elevation (defined as 1 grade shift [ie, increase] or $2 \times$ previous value) with confirmed changes outside of the normal range in other laboratory parameters suggestive of worsening hepatic function (abnormal prothrombin time ≥ 2 seconds over study baseline or international normalized ratio [INR] ≥ 0.5 over study baseline, and abnormal serum albumin ≥ 1 g/dL below study baseline or elevated serum lactate levels [if available], defined as $2 \times$ ULN).

If the first of two consecutive results is in the double-blind phase and the second is out of the double-blind phase (ie, in the open-label or TFFU phase), then the result will be considered to be confirmed in the double-blind phase (assuming both values meet the criterion). And if the criterion is met by the last value in the double-blind phase, and no assessments are available after due to the subject exiting the study or data not yet available (eg, due to the data-cut), then the result will also be considered to be confirmed.

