7.11. Changes From Protocol-Specified Safety Analyses

Baseline for BMD assessments for spine and whole body (via DXA scan) and serum bone biochemical markers will be calculated only using the Baseline Visit value, instead of taking the mean of the Screening and Baseline Visit values.

Treatment-emergent AEs and lab abnormalities were defined as any AE or lab abnormality that began on or after the study drug start date and no later than the study drug stop date in the protocol for those who discontinued study drug. This has been updated in this SAP to any AE with onset date on or after the blinded study drug start date and no later than the minimum of the blinded study drug stop date + 3 days and the first dose date of open-label study drug, if applicable for the double-blind phase, and to any AE with onset date on or after the open-label study drug start date and no later than the minimum of the open-label study drug stop date + 3 days for the open-label phase. This change was made as labs performed 1-2 days after study drug stopped were being excluded causing the measurement for the timepoint to be missed, even though protocol specified visit windows allowed for labs to be performed in a short period after the study drug was stopped.

Percent change from baseline in bone mineral density of lumbar spine was compared between treatment groups using ANOVA with treatment as a fixed effect, instead of the Wilcoxon rank sum test, to be consistent with other studies.

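### SAP 7.2.3 requires a PT or INR change and an albumin or lactate change for its second ALT-flare criterion; the protocol accepts any one of them

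*SAP*

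**What the plan says.** SAP 7.2.3 summarises ALT flare and exacerbation of hepatitis by treatment group in the Safety Analysis Set, on treatment in the double-blind phase and off treatment. A subject counts by either of two criteria. The first is ALT above both 2 × study baseline and 10 × ULN. The second is a confirmed ALT elevation (a one-grade increase or 2 × the previous value) with confirmed abnormal changes in tests of hepatic function. For those tests the SAP gives PT or INR thresholds and then continues: "over study baseline, and abnormal serum albumin ≥ 1 g/dL below study baseline or elevated serum lactate levels [if available".

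The protocol has the same first criterion. Its second criterion lists the same tests without *and*:

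- Section 7.6.6, flare definition: "abnormal PT ≥ 2 seconds or INR ≥ 0.5 over baseline, abnormal serum albumin", with the list then closed by *or* before lactate.
- Section 7.3, events that must be reported as SAEs: "abnormal PT ≥ 2 seconds or INR ≥ 0.5 over baseline, abnormal serum albumin ≥ 1 g/dL below baseline or elevated serum lactate levels".
- Section 7.6.6.1, management on study drug: "INR ≥ 0.5 above baseline, abnormal albumin ≥ 1 g/dL decrease from baseline or elevated serum lactate levels".
- Section 7.6.6.2, management after stopping: "abnormal PT ≥ 2 secs above baseline, abnormal albumin ≥ 1 g/dL below baseline or elevated lactate levels".

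SAP 7.1.4 identifies SAEs by the protocol's definitions, so SAE reporting keeps the protocol rule.

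**The concern.** The SAP follows the protocol's flare definition almost phrase by phrase, except for this connector. Programmed as punctuated, the flare table uses a stricter rule than the one sites apply when they manage a flare or report an SAE. The discrepancy can only lower the count.

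At stake is consistency within one report on a liver-safety outcome in children. A child who meets the protocol's second criterion on one test alone would be in the SAE table for the double-blind phase and absent from the flare table. Albumin is the clearest case because it is in the chemistry panel at every treatment and follow-up visit, so it is the hepatic-function change that scheduled visits can detect.

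**Working it through.** The plan gives no figure to reproduce; the check is logical.

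**Inputs.** Four yes/no findings (PT, INR, albumin, lactate), each meaning a confirmed abnormal change past its threshold. Assume a confirmed ALT elevation that does not meet the first criterion; if it does, the child is counted under both documents whatever the other tests show.

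**Patterns.** At least one abnormal test out of four gives 2⁴ − 1 = 15 patterns. With lactate unavailable there are 2³ − 1 = 7.

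**Protocol.** Any one test suffices: 15 of 15, or 7 of 7 without lactate.

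**SAP as punctuated.** At least one of {PT, INR} gives 2² − 1 = 3 options, and at least one of {albumin, lactate} gives 3, so 3 × 3 = 9 of 15. The 15 − 9 = 6 missed patterns are PT only, INR only, PT with INR, albumin only, lactate only, and albumin with lactate. Without lactate, 3 × 1 = 3 of 7 count.

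**Other literal groupings of the same words:**

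| Rule | Counted of 15 | Counted of 7 (no lactate) | Albumin alone counted? |
|---|---|---|---|
| Protocol: any one | 15 | 7 | yes |
| (PT or INR) and (albumin or lactate) | 9 | 3 | no |
| ((PT or INR) and albumin) or lactate | 11 | 3 | no |
| PT or (INR and albumin) or lactate | 13 | 5 | no |

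PT and INR are two expressions of one test. Treated as one, there are 2³ − 1 = 7 patterns, of which the SAP as punctuated counts 3. The patterns are not equally likely, so these counts describe the rule and do not estimate a frequency.

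**Illustration (assumed values).** ALT goes from 4 × ULN (Grade 2) to 7 × ULN (Grade 3), confirmed. Albumin goes from 4.4 to 3.3 g/dL, a fall of 1.1, below an assumed lower limit of 3.5, confirmed. PT, INR and lactate are normal. The first criterion fails because 7 < 10. The protocol's second criterion is met, so this is a flare and an SAE. The SAP's second criterion is not met.

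**Size per child.** SAP 1.3 gives 89 treated. The split by arm is not stated; at 2:1, 89 × 2/3 ≈ 59 on TDF and 30 on placebo. One missed child is 1/59 = 1.7% or 1/30 = 3.3%. The documents give no rate for events meeting only the second criterion, so no expected number is offered.

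**The case against.** The strongest reply is that *and* is a loose list word. Read that way, the SAP equals the protocol and nothing is lost. A drafting slip is the likelier explanation, since the rest of the sentence tracks the protocol so closely. This stands as an account of intent, but none of the three literal groupings gives the protocol's rule, and the programmer should not have to guess.

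Three stronger readings are tempting, and the documents do not support them.

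- *That albumin-only worsening is never counted.* It is counted whenever ALT meets the first criterion. The loss is confined to ALT rises below that threshold.
- *That the sponsor changed the definition without declaring it.* SAP 7.11 does not mention the flare definition; its entries include "Percent change from baseline in bone mineral density of lumbar spine was compared between treatment groups using ANOVA with treatment as a fixed effect". But 7.11 covers changes to safety analyses that the protocol specified, and Protocol 8.9 specifies no flare summary. Silence there is weak evidence of anything.
- *That the SAP rule will fail because PT/INR is missing.* Appendix 2 says "PT/INR will be performed at the Screening and Baseline Visits, then as a reflex test in subjects experiencing exacerbation of hepatitis thereafter", and Section 6.3.1 has PT/INR in follow-up only as a "reflex test in case of post-treatment exacerbation of hepatitis". Yet Sections 7.6.6.1 and 7.6.6.2 recommend recalling exactly this child and drawing PT/INR, lactate and albumin. Where that is followed, the SAP rule fails because PT/INR is normal, not because it is absent.

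Existing coverage also counts. In the double-blind phase the SAE is tabulated by arm (SAP 7.1.6). A fall in albumin from normal to below normal is Grade 2 under age 16, so it is tabulated as a treatment-emergent abnormality, as is a one-grade ALT rise (SAP 7.2.2). Off-treatment data go to listings (SAP 7). What could be lost is the combined flare label. Entry criteria exclude low albumin, prolonged PT and past decompensation, so such events should be uncommon.

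**Conclusion.** The point holds as a mismatch of definitions. Followed as written, SAP 7.2.3 leaves out children who miss the first criterion and whose confirmed abnormal change lies only in PT/INR or only in albumin/lactate. The protocol calls the same children flares and requires an SAE report. Albumin alone is omitted under every literal grouping tried.

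The consequence is small. The number of children is unknown and may be zero; each would move an arm's flare incidence by about 1.7 (TDF) or 3.3 (placebo) percentage points, assuming a 2:1 split of the 89 treated. The table is descriptive. Efficacy endpoints, hypothesis tests and site actions are unaffected. The conclusion assumes that the programmer follows the printed connector.

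**What to change.** In the second criterion of SAP 7.2.3, replace the joined clause with a list headed *at least one of*, each item confirmed and outside the normal range:

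- PT at least 2 seconds over study baseline;
- INR at least 0.5 over study baseline;
- serum albumin at least 1 g/dL below study baseline;
- elevated serum lactate (if available), defined as 2 × ULN.

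Keep the lactate item as defined. Protocol 7.3 and 7.6.6 and SAP 7.2.3 all set it at 2 × ULN; the strict *greater than* appears only in the management text of 7.6.6.1 and 7.6.6.2, and importing it would be a second silent change.

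If the stricter rule is intended, say so with the reason, and show the count under the protocol definition beside it.

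The cost is one clause before database finalization and no new data. The flare count may rise slightly.
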